2.2.2 Randomization and Blinding

This study does not employ randomization. This is an open-label study.

2.2.3 Sample Size Determination

A sample size of approximately 35 evaluable subjects (i.e. completing the week 16 study visit without any major deviations which may interfere with study endpoints) was set for feasibility and to ensure a reasonable dataset to evaluate the Orenitram dose achieved, the clinical response to Orenitram after an induction period with Remodulin, and to assess the safety and tolerability of Orenitram after induction therapy with Remodulin. No formal sample size computation was performed with respect to the primary endpoint.

2.3 Study Endpoints

2.3.1 Primary Endpoint

The primary efficacy endpoint is the percentage of subjects achieving an Orenitram dose of 4 mg TID (or a total daily dose of 12 mg) or higher at Week 16 (or a dose of 0.057 mg/kg TID [or a total daily dose of 0.171 mg/kg] or greater for subjects <70 kg).

The prescribed total daily dose will be used for the primary efficacy endpoint.

2.3.2 Secondary Endpoints

2.3.2.1 Safety Endpoints

Safety will be assessed using the Prostanoid Adverse Event (AE) scores captured by the AE Bothersome Survey at Baseline, the Transition Visit, and Week 16/Early Study Withdrawal.

The Investigator will administer the AE Bothersome Survey (provided in protocol Appendix E) at time points listed in Table 1 to collect information about prostanoid-related effects experienced by the subject, including headache, diarrhea, nausea, flushing, jaw pain, extremity pain and vomiting. For each prostanoid-related effect, whether the patient has experienced the effect, the degree of bothersome (from 1 - bothers me a lot to 4 - not at all bothersome), and days experiencing it (1 to 7) will be recorded.

Other safety assessments including the incidence of adverse events, clinical laboratory tests, vital signs, and physical examinations are described in Section 3.7.

2.3.2.2 Efficacy Endpoints

The secondary efficacy endpoints are to assess the effect of treatment with Orenitram after an induction period with Remodulin on the following parameters:

- Change in 6-Minute Walk Distance (6MWD) from Baseline to the Transition Visit and Week 16
- Change in Borg dyspnea score from Baseline to the Transition Visit and Week 16
- Change in World Health Organization (WHO) Functional Classification (FC) from Baseline to the Transition Visit and Week 16
- Change in N-terminal pro-brain natriuretic peptide (NT-proBNP) levels from Baseline to the Transition Visit and Week 16

5. Change in Echocardiographic parameters from Baseline to the Transition Visit and Week 16

Echocardiogram (ECHO) examinations as assessed by central reader will be conducted at the time points listed in Table 1. Several echocardiographic parameters will be collected, including: right atrial area (cm²), tricuspid annular plane systolic excursion (mm), RV free wall strain (%), RV/left ventricular ratio at diastole, RV diastole (mm), LV diastole (mm), Eccentricity Index systole, Eccentricity Index diastole, RV Myocardial Performance Index; Pulmonary Artery Acceleration Time (msec) and presence of PV Notching (Non-evaluable, Present or Not Present); LVOT dimension (mm), LVOT vti (cm), ECHO Heartrate (bpm), cardiac output (Doppler method) (L/min) and presence of pericardial effusion (Present/ Not Present)

- 6. Change in PAH symptom score from Baseline to the Transition Visit and Week 16
- 7. The percentage of subjects that improve in each of the following 4 individual clinical parameters at Week 16 (6MWD, NT-proBNP, WHO FC, right atrial area) to a lower risk stratum, as defined by the 2015 European Society of Cardiology guidelines, compared to Baseline
- The percentage of subjects that meet each of the following 4 individual clinical parameters at Week 16 in the low risk category, as defined by the 2015 European Society of Cardiology guidelines: 6MWD >440 meters, serum NT-proBNP <300 ng/L, WHO FC I or II, and right atrial area <18 cm²
- 9. The percentage of subjects that either achieve an Orenitram dose of 4 mg TID (or a total daily dose of 12 mg) or higher at Week 16 (or a dose of 0.057 mg/kg TID [or a total daily dose of 0.171 mg/kg] or greater for subjects <70 kg) or the percentage of subjects that achieve an Orenitram dose ≥2 mg TID and <4 mg TID (or a total daily dose ≥6 mg and <12 mg) at Week 16, with at least 2 of the following 3 clinical parameters at Week 16 calculated and summarized: 6MWD increase by ≥10% or ≥30 meters from Baseline, serum NT-proBNP reduction >30% from Baseline, or WHO FC I or II. This will performed using both prescribed total daily dose as well as actual dose taken.
- 10. The percentage of subjects that successfully transitioned to Orenitram at any dose and were successfully maintained on therapy at Week 16
- 11. Change in Subjects' Treatment Satisfaction Questionnaire for Medication (TSQM) responses and Health-related quality of life (emPHasis-10) questionnaires from Baseline to the Transition Visit and Week 16

The prescribed total daily dose will be used for secondary efficacy endpoints when applicable, unless otherwise stated.

TSQM

The questionnaire is provided in protocol Appendix G. The TSQM (version 1.4) comprises 14 items across four domains focusing on effectiveness (three items Q1-Q3), side effects (five items Q4-Q8), convenience (three items Q9-Q11), and global satisfaction (three items Q12-Q14) of the medication over the previous 2–3 weeks, or since the patient's last use. Except for item 4 (presence of side effects; yes or no), all items have five or seven responses, scored from one (least satisfied) to five or seven (most satisfied). Item scores are summed to give four

domain scores, which are in turn transformed to a scale of 0-100. Item 4 is not included for scoring. If an item score is missing and half of the items in the domain are complete, domain scores may be imputed from the person-specific mean score of completed items (i.e., the domain scores will be calculated as the total score of the completed items divided by the possible maximum total score of the completed items and times 100). For example, if a subject has Q1 = 5, Q2 = 2 and Q3 is missing, then domain score effectiveness = (5+2)/(7+7)*100 = 50. The calculated domain scores will be listed.

emPHasis-10

The questionnaire is provided in protocol Appendix H. The emPHasis-10 comprises 10 items. Each item has a score scale of 0-5. The total score will be calculated as

Total score of answered questions X 10 / Number of answered questions.

The range of the total score is 0-50. If the number of answered questions is less than 7, the total score will be considered missing. The calculated total score will be listed.

Exploratory Efficacy Endpoints

The exploratory efficacy endpoints will be prespecified in this document but will be summarized at a later time by the study sponsorD.

REVEAL 2.0 risk score and French non-invasive risk score (Boucly 2017) will be summarized at Baseline, the Transition Visit, and Week 16. Change from Baseline to Transition, Baseline to Week 16, and Transition to Week 16 will also be summarized.

For subjects who consent to the optional pharmacogenomics (genetic/ribonucleic acid [RNA] testing) and biomarker testing, Baseline pharmacogenomics will be evaluated. Additionally, evaluation of biomarkers at Baseline, the Transition Visit, and Week 16, and change from Baseline to Transition, Baseline to Week 16, and Transition to Week 16 will be performed.

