Appendix G. Treatment Satisfaction Questionnaire for Medication (TSQM) (Version 1.4)

Instructions: Please take some time to think about your level of satisfaction or dissatisfaction with the medication you are taking in this clinical trial. We are interested in your evaluation of the effectiveness, side effects, and convenience of the medication *over the last two to three weeks, or since you last used it.* For each question, please place a single check mark next to the response that most closely corresponds to your own experiences.

1.	How satisfied or condition?	dissatisfied are you with the ability of the medication to prevent or treat your
		1 Extremely Dissatisfied 2 Very Dissatisfied 3 Dissatisfied 4 Somewhat Satisfied 5 Satisfied 6 Very Satisfied 7 Extremely Satisfied
2.	How satisfied or	dissatisfied are you with the way the medication relieves your symptoms?
		1 Extremely Dissatisfied 2 Very Dissatisfied 3 Dissatisfied 4 Somewhat Satisfied 5 Satisfied 6 Very Satisfied 7 Extremely Satisfied
3.	How satisfied or working?	dissatisfied are you with the amount of time it takes the medication to start
		1 Extremely Dissatisfied 2 Very Dissatisfied 3 Dissatisfied 4 Somewhat Satisfied 5 Satisfied 6 Very Satisfied 7 Extremely Satisfied
4.	As a result of tak	ring this medication, do you experience any side effects at all?
		1 Yes 0 No (if No, then please skip to Question 9)

5.	How bothersome are the side effects of the medication you take to treat your condition?
	 □ 1 Extremely Bothersome □ 2 Very Bothersome □ 3 Somewhat Bothersome □ 4 A Little Bothersome □ 5 Not at All Bothersome
6.	To what extent do the side effects interfere with your physical health and ability to function (ie, strength, energy levels, etc)?
	 □ 1 A Great Deal □ 2 Quite a Bit □ 3 Somewhat □ 4 Minimally □ 5 Not at All
7.	To what extent do the side effects interfere with your mental function (ie, ability to think clearly, stay awake, etc)?
	☐ 1 A Great Deal ☐ 2 Quite a Bit ☐ 3 Somewhat ☐ 4 Minimally ☐ 5 Not at All
8.	To what degree have medication side effects affected your overall satisfaction with the medication?
	☐ 1 A Great Deal ☐ 2 Quite a Bit ☐ 3 Somewhat ☐ 4 Minimally ☐ 5 Not at All
9.	How easy or difficult is it to use the medication in its current form?
	☐ 1 Extremely Difficult ☐ 2 Very Difficult ☐ 3 Difficult ☐ 4 Somewhat Easy ☐ 5 Easy ☐ 6 Very Easy ☐ 7 Extremely Easy
10	. How easy or difficult is it to plan when you will use the medication each time?

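### A subject who reports no side effects on the TSQM gets no side-effects domain score under the SAP's rules, so that domain describes only subjects who have side effects

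*SAP*

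**What the plan says.** The TSQM (version 1.4) is completed at Baseline, the Transition Visit and Week 16/Early Study Withdrawal. Change from Baseline to the Transition Visit and to Week 16 is secondary efficacy endpoint 11 in SAP 2.3.2.2. For visits after transition, SAP 3.4.2 adds change from the Transition Visit.

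Four statements bear on the side-effects domain:

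- **The skip.** In Protocol Appendix G, the second option of Question 4 reads "No (if No, then please skip to Question 9". Questions 5 to 8 are then blank by design.
- **The domain.** SAP 2.3.2.2 assigns Questions 4 to 8 to side effects and adds "Item 4 is not included for scoring". The scored items are therefore Questions 5 to 8.
- **The missing-item rule.** A domain score may be imputed under one condition: "If an item score is missing and half of the items in the domain are complete".
- **The formula for that case.** The score is "the total score of the completed items divided by the possible maximum total score of the completed items and times 100".

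The SAP assigns no score to a subject who answers No to Question 4.

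**The concern.** The blank items are not ordinary missing data. They arise exactly when the subject gives the best possible answer about side effects. Under rules that treat a blank as missing and score only domains at least half complete, the subjects with the best tolerability leave the domain score, and those who remain all have side effects.

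Two results are at stake. The domain mean at a visit would be read as describing everyone who completed the questionnaire, when it describes only those with side effects. And a change score needs both visits, so a subject who moves from no side effects to some, or from some to none, contributes nothing, although those are the clearest shifts in tolerability that the domain could record. Tolerability is named in the secondary objective (SAP 2.1.2) and in the clinical hypothesis (Protocol 1.4).

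**Working it through.** **1. The SAP's own figure.** For effectiveness with Q1 = 5, Q2 = 2 and Q3 missing, the formula gives (5 + 2)/(7 + 7) × 100 = 50. This matches the SAP's worked example ("then domain score effectiveness = (5+2)/(7+7)*100 = 50"), so the rule is being read as intended.

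**2. The same rule after a No at Question 4.**

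- Scored items complete: 0 of 4 = 0%. Counting Question 4 as a completed item: 1 of 5 = 20%. Both are below half, so the imputation rule does not apply.
- The formula itself would be 0/0, which is undefined.
- The last-observation-carried-forward rule in SAP 3.4.2 covers 6MWD, WHO FC, NT-proBNP and echocardiographic parameters, not the TSQM. Protocol 10.3.2.2.1 says only that TSQM responses are summarized.

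The score is uncomputable on either count of items, and nothing else fills it.

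**3. The top of the scale.** The best answer to each of Questions 5 to 8 is 5, which gives (5 + 5 + 5 + 5)/20 × 100 = 100. A subject with no side effects is logically no worse off than that.

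**4. Effect on a visit mean.** Let k of N subjects answer No and let the others average m. The plan reports m. With No valued at 100, the mean of all subjects is m + (k/N)(100 − m), so the plan's figure is too low by (k/N)(100 − m). N = 35 is the approximate evaluable number in SAP 2.2.3. The values of k and m are assumptions.

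| Answering No | m = 50 | m = 60 | m = 70 |
|---|---|---|---|
| 4 of 35 | 5.7 | 4.6 | 3.4 |
| 7 of 35 | 10.0 | 8.0 | 6.0 |
| 10 of 35 | 14.3 | 11.4 | 8.6 |

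For example, 10/35 × (100 − 50) = 14.3. The range is about 3 to 14 points. Exact shares of 10% and 30%, without rounding to whole subjects, give 3 to 15.

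**5. Effect on change scores.** With shares p0 at Baseline and p1 at Week 16 answering No independently, the proportion without a change score is 1 − (1 − p0)(1 − p1). For assumed shares of 50% and 20%, this is 1 − 0.5 × 0.8 = 60%, or 21 of 35. Without independence it lies between 50% and 70%.

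**6. Direction of bias in change.** With No valued at 100, three kinds of subject are lost:

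- No at Baseline, Yes later: a fall is lost, so the reported change looks too favorable.
- Yes at Baseline, No later: a rise is lost, so the reported change looks too unfavorable.
- No at both visits: a zero change is lost.

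The net direction depends on the mix, which the documents do not give.

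**The case against.** The case for treating this as minor is substantial, and much of it stands.

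- **Tolerability is measured better elsewhere.** The AE Bothersome Survey covers seven prostanoid effects at the same three visits, and SAP 3.7.1.1 reports the percentage with each effect and a burden score. SAP 3.7.1 reports prostanoid AEs by treatment phase and maximum severity. The protocol synopsis lists the TSQM under clinical response, not under safety and tolerability. This stands and limits the consequence.
- **The No answers may still be visible.** SAP 3.4.2 summarizes TSQM responses, so Question 4 may be tabulated as an item. This stands in part. The SAP commits to reporting the first question of the AE Bothersome Survey but makes no such commitment for Question 4, and a tabulated item does not restore the domain score or its change.
- **The SAP never calls the score missing, and the programming specifications are a separate document (SAP 6).** They may contain a rule. But the published rules, followed literally, give no score, and a scoring convention belongs in the SAP. For emPHasis-10, the SAP does say when the score is missing.
- **A score of 100 at Baseline is awkward.** Baseline precedes Remodulin, inclusion criterion 6 admits subjects on no PAH therapy, and Appendix G asks about the medication taken in the trial. A perfect score for a drug not yet taken builds in a later fall. This stands, and the fix has to deal with it.

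A reader might also infer that the plan hides a real deterioration of a definite size. If the scored subjects average 65, the all-subject mean is 65 + 35p. If p falls from 50% to 10%, that mean goes from 82.5 to 68.5, a fall of 14 points that the mean of scored subjects does not show. The arithmetic is right, but the documents support neither the 65 nor either share, so 14 points is only a hypothetical.

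**Conclusion.** The concern holds for the side-effects domain score and its change. Under SAP 2.3.2.2 as written, a subject who answers No to Question 4 has no computable score. Each visit mean therefore covers only subjects with side effects and is biased toward worse tolerability. Anyone answering No at either visit has no change score, and the direction of the resulting bias in change is not fixed.

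The understatement at a visit is about 3 to 14 points. That rests on assumed No shares of about 10 to 30%, assumed observed means of 50 to 70, and a value of 100 for No. The true share is unknown.

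A reader might infer that the trial's tolerability evidence, or the whole TSQM endpoint, is compromised. The documents do not support that. The other three TSQM domains, the AE Bothersome Survey and the primary endpoint are unaffected, and no formal testing is planned (SAP 3.1.6).

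**What to change.** Add to SAP 2.3.2.2: *If Q4 = No, the side-effects domain is set to 100, the value the SAP formula gives for the best answer to all of Q5-Q8; if Q4 = Yes, Q5-Q8 are scored.* Report the number and percentage with Q4 = No at each visit beside the domain score.

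Because of the Baseline difficulty, present the Transition Visit and Week 16 scores and the Transition-to-Week 16 change alongside change from Baseline. SAP 3.4.2 already provides for that later change. Flag the Baseline scores of subjects on no PAH medication, or show them separately.

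The cost is a short SAP addition before database lock, a line or two of programming and one extra Baseline display, with no new data. The downside is a visible ceiling at 100, which the percentage answering No will explain.

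### The SAP's TSQM formula cannot produce its stated 0–100 scale, and subjects who report no side effects get no side-effects score

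*SAP*

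**What the plan says.** SAP 2.3.2.2 lists change in TSQM responses among the secondary efficacy endpoints and then describes the scoring. Apart from the yes/no Question 4, items are "scored from one (least satisfied) to five or seven (most satisfied"). They are summed into "domain scores, which are in turn transformed to a scale of 0-100". No equation is given for a domain with all items answered.

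An equation is given for a partly answered domain. It applies under this condition: "If an item score is missing and half of the items in the domain are complete". The score is then the completed sum over its largest possible value, times 100. For Q1 = 5, Q2 = 2 and Q3 missing, the SAP concludes: "then domain score effectiveness = (5+2)/(7+7)*100 = 50".

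The side-effects domain is Questions 4 to 8, but "Item 4 is not included for scoring". In the questionnaire itself (Protocol Appendix G), a subject who answers No to Question 4 is sent straight to Question 9.

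On reporting, SAP 2.3.2.2 says: "The calculated domain scores will be listed". SAP 3.4.2 has TSQM responses summarised by visit, with change from Baseline and from the Transition Visit.

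**The concern.** There are two separate problems.

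First, a ratio of sum to maximum reaches 0 only if items can score 0. TSQM items cannot, so the formula and the stated scale disagree. Depending on how complete forms are handled, either complete and partial forms are on different scales, or no domain is on the scale the SAP names. In the first case a subject's change can come from a skipped item rather than from a changed answer.

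Second, the side-effects domain has no score for exactly the subjects who report no side effects. Tolerability is part of the secondary objective. A subject whose side effects resolve by Week 16 leaves the change score instead of counting as improved, and the visit-by-visit summaries describe different subsets without saying so.

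**Working it through.** **Inputs.** From SAP 2.3.2.2: item minimum 1, maximum 5 or 7, and the four domains. From Protocol Appendix G: Q1–Q3, Q9–Q11 and Q14 have seven responses; Q5–Q8, Q12 and Q13 have five.

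Let n be the number of items completed, S their sum and M their maximum possible sum.

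- Printed formula: P = 100 × S/M
- Formula that does run from 0 to 100: R = 100 × (S − n)/(M − n)
- Difference: P − R = 100 × n(M − S)/[M(M − n)]

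**Step 1, the SAP's example.** P = 100 × 7/14 = 50.0, which matches. Filling Q3 with the subject's mean of 3.5 gives the same value, 10.5/21 = 50.0. On a true 0–100 scale, R = 100 × (7 − 2)/(14 − 2) = 41.7, and with Q3 = 3.5 again (10.5 − 3)/18 = 41.7. The gap is 8.3 points.

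**Step 2, the floor of the printed formula** (every completed item at 1):

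| Domain | Partial form, lowest P | Complete form, lowest P if the same ratio is used | Partial form, P − R at worst / middle / best answers |
|---|---|---|---|
| Effectiveness, convenience | 2/14 = 14.3 | 3/21 = 14.3 | 14.3 / 7.1 / 0 |
| Side effects | 2/10 or 3/15 = 20.0 | 4/20 = 20.0 | 20.0 / 10.0 / 0 |
| Global satisfaction | 2/12 = 16.7 or 2/10 = 20.0 | 3/17 = 17.6 | 16.7–20.0 / 8.3–10.0 / 0 |

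The emPHasis-10 rule in the same section shows the contrast. There, "Each item has a score scale of 0-5", so all zeros give 0 × 10/10 = 0 and all fives give 50 × 10/10 = 50. That agrees with the SAP's statement: "The range of the total score is 0-50".

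**Step 3, the two readings for complete forms.**

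- *Complete forms rescaled to a true 0–100.* Answers 4, 4, 4 score (12 − 3)/(21 − 3) = 50.0, while 4, 4, missing scores 8/14 = 57.1. The skipped item alone adds 7.1 points. The number of partial forms is not given. Assuming 1, 3 or 5 partial forms among 35 scored subjects, all with middle answers, the group mean moves by 7.14k/35 = 0.2, 0.6 or 1.0 points for effectiveness and 10.0k/35 = 0.3, 0.9 or 1.4 for side effects. The side-effects figures rise in proportion if fewer than 35 subjects have a score.
- *Printed ratio used throughout.* Differences shrink by (M − n)/M: 18/21 = 0.857, 16/20 = 0.800 and 14/17 = 0.824. A 20-point change becomes 17.1 (effectiveness, convenience), 16.0 (side effects) or 16.5 (global satisfaction). Direction and rank order are kept for complete forms.

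**Step 4, Question 4 answered No.** Questions 5–8 are blank, so 0 of 4 scored items are complete, or 1 of 5 if Question 4 is counted. Both are below half, and the formula itself becomes 0/0. The last-observation-carried-forward rule in SAP 3.4.2 does not name the TSQM. No score results. If a share p answers No at each of two visits, the change score exists for between max(0, 1 − 2p) and 1 − p of subjects, depending on overlap. For assumed p of 10%, 30% and 50% this is 80–90%, 40–70% and 0–50%.

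**The case against.** The strongest reply to the first problem is that the SAP prints one formula and it can be applied unchanged to complete forms. All forms would then share one percent-of-maximum scale, and only the 0–100 label would be wrong. SAP section 6 also refers to separate programming specifications, not available here, which may give the complete-form equation. This stands as far as it goes: the mixed-scale harm is conditional on a reading the SAP does not state. Neither route makes the SAP's own example fit its own scale.

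On the endpoint, the SAP speaks of TSQM responses and says only that domain scores will be listed. A summary of domain scores is the natural reading, since the SAP defines them at length, but it is not stated by name. Item responses are unaffected.

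On Question 4, the SAP never says the domain is missing; that is deduced from its rules, and items skipped on instruction could be called not applicable. The label does not matter, because no value is assigned either way. SAP 3.1.5 already provides category percentages and non-missing counts, so some of the figures requested below should appear anyway. The AE Bothersome Survey separately records which subjects have each prostanoid effect.

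A last point is that person-mean imputation and a completed-items formula differ where five- and seven-point items are mixed. With Q12 = Q13 = 5 and Q14 missing, imputing Q14 = 5 gives (15 − 3)/(17 − 3) = 85.7, against 100 on completed items only. The SAP's own spelled-out formula works on completed items and also gives 10/10 = 100, so the formula proposed below keeps the SAP's choice.

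**Conclusion.** Both problems hold. The printed formula has a floor of 14.3 to 20.0 where the SAP states 0, and its example gives 50 where a 0–100 scale gives 41.7. That follows from the SAP's text and the questionnaire alone. Whether the consequence is mixed scales or uniform shrinkage to 80–86% depends on the unprinted complete-form equation. For Question 4 answered No, the rules yield no side-effects score, so that domain's summaries and changes cover only subjects who report side effects.

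The size is modest. Group means move little under the assumed counts of partial forms; individual scores and changes can move more. The shares answering No are assumptions, since the documents give none. SAP 3.1.6 plans no formal testing, and the primary endpoint does not use the TSQM. This should be corrected before the scores are derived, but it does not threaten the trial's main result.

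**What to change.** Print one formula for complete and partial domains: (sum of completed items − number completed) / (maximum possible sum of completed items − number completed) × 100. Change the worked example from 50 to 41.7. Say whether the completeness condition means at least half of the scored items.

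For the side-effects domain, state what happens when Question 4 is No:

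- Report the number and percentage answering No at each visit beside the domain summary.
- Label that summary as conditional on reporting side effects.
- Give the number of subjects behind each change score.

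Any value assigned to No, such as 100, should be a sensitivity summary only, with particular care at Baseline. Under Protocol 7.2 the Baseline form is completed before Remodulin starts, although Appendix G asks about the trial medication, and under inclusion criterion 6 (Protocol 4.1) some subjects may be on no PAH therapy. Scoring No as 100 there could build in an apparent worsening.

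The cost is SAP wording and a few lines of derivation code; no new data are needed.
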